1.1.2 Secondary Objectives

- To determine best response rates according to International Myeloma Working Group criteria after 8 cycles of CRd combination therapy
- To determine progression free survival (PFS)
- To determine duration of response (DOR)
- To determine overall survival (OS)
- To evaluate biological activity of carfilzomib and correlate to clinical outcomes, including gene expression profiling on pre- and post-carfilzomib exposure bone marrow samples
- To assess the impact of minimal residual disease by flow cytometry and PET/CT in relation to outcome

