1.2.8 Proposed Study Investigation with Correlative Studies

Given carfilzomib's potent anti-myeloma activity and lack of peripheral neuropathy, we propose a phase II investigation of combination therapy (Cycles 1-8 carfilzomib, lenalidomide, dexamethasone) in newly diagnosed MM patients followed by extended dosing with lenalidomide (days 1-21 of 28 day cycle) for 12 cycles. Patients will be enrolled on study to determine if the CRd 3 drug-combination demonstrates a rate of grade 3 or worse neurologic toxicity lower than 10% in the first two completed cycles. After 4 cycles, transplant eligible patients will undergo autologous stem cell harvesting. After 8 cycles, patients achieving SD or better will proceed to extended dosing with lenalidomide. Patients not achieving SD will be off treatment. Response criteria is outlined in Section 5.3. Proposed correlative studies include gene expression profiling on purified CD 138 + pre- and post- carfilzomib plasma cells, identification of potential biomarkers (blood, urine, bone marrow aspirates), proteasome quantification and activity, ubiquitination assays, and effects on downstream signaling targets. Patients will also undergo evaluation for minimal residual disease at regular interval time points, using multi-parametric flow cytometry, FDG PET-CT, and detection of clonality using heavy and/or light chain immunoglobulin rearrangement. Effective with Amendment L (version date 07/15/2015), bone marrow aspirate and biopsy will be obtained for research studies at the discretion of the PI.

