5.1.1 Bone Marrow and Peripheral Blood

- a. During extension phase lenalidomide, bone marrow biopsy and aspirates are optional for those patients that are MRD negative at the end of cycle 8 regardless of response.
- b. Patients may be asked to undergo bone marrow at progression of disease at the discretion of the PI.
- c. Collection of bone marrow, sorting of bone marrow and storage of bone marrow samples is

outlined in **Appendix B** and Section **5.2.1**.

- d. Correlative studies associated with bone marrow specimen will be performed and related to clinical outcome if the results of the study indicate a clinical or translational rationale for analyzing the samples. Such studies may include but are not limited to the following:
- i. Pathology/Immunohistochemistry: Bone marrow biopsy and aspirate will be sent to Clinical Center Department of Laboratory Medicine, Hematology Section for morphological evaluation by [name] and [name], PhD. Immunohistochemical staining will be performed under the direction of [name]. Plasma cell burden will be assessed using immunohistochemistry markers such as CD 138, light chains, CD56 etc. Plasma cells and microenvironment interactions will also be assessed using various immunohistochemistry markers for osteoblasts, osteoclasts, stromal cells and proteasomes.
 - ii. Minimal Residual Disease: Flow cytometry: Immunophenotyping of aberrant plasma cells by flow cytometry currently involves, but is not limited to, the use of the following reagents: CD138, CD19, CD45, CD38, and CD56. Characteristic changes in immunophenotypically abnormal plasma cells (CD138 positive) include but are not limited to absent CD19 and CD45, decreased CD38, and increased CD56. These studies will be performed under the direction of [name] of the flow cytometry unit in the NCI Laboratory of Pathology
 - iii. FISH and cytogenetics: Interphase FISH/cytogenetics will be performed on patients enrolled in this protocol under the direction of [name] of the Molecular Diagnostics Core Laboratory of the NCI Branch. (**NOTE:** [name] no longer at NIH/NCI, her involvement ended and these studies no longer being done as of Amendment M.)

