Samples may be collected within 2 days prior to each of the above time points during the induction phase; and within 7 days prior to each of the above time points during the extension phase I and II phase. The amount of urine collected will be dictated by the number of experiments to be performed.

All Samples:

- a. Collection and storage of peripheral blood and urine outlined in [Appendix C](#). Sample Requirements and Handling: The date and exact time of each blood draw should be recorded on the sample tube. Serum samples should be kept at room temperature for 30-60min prior to being refrigerated. Please e-mail [name] at [contact] and [name] [contact] at least 24 hours before transporting samples (the Friday before is preferred).

For sample pickup, page [name].

For immediate help, call [contact] (main blood processing core number) or, if no answer, [contact] (main clinical pharmacology lab number).

For questions regarding sample processing, contact [name] by e-mail or at [contact].

- b. Peripheral blood and/or urine samples from patients will be analyzed for potential serum or urine biomarkers as well as drug concentrations, and correlated to clinical outcomes if the results of the study indicate a clinical or translational rationale for analyzing the samples. Such biomarkers may include but are not limited to:
 - i. Peripheral blood flow cytometry assessing for circulating plasma cells under the direction of [name].
 - ii. Subunit profiling and activity of circulating proteasomes by enzyme-like

- iii. immunosorbent assay
- iii. Apoptosis assays pre and post-carfilzomib to identify necrotic or late stage apoptotic cells
- iv. Immunolocalization studies
- v. Markers of bone turnover and disease activity
- vi. Bone marrow, blood and urine samples, and associated clinical lab data will be sent to Adaptive Biotechnologies Corp for deep sequencing of the VDJ sequence.
- vii. Peripheral blood will be assessed for immune cell populations including, but not limited to T cells (CD4 and CD8), LGL, and NK cells using flow cytometry under the direction of [name]

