10.3.2 Analysis of the Secondary Endpoints

Secondary endpoints are to estimate overall response rates (ORR) according to International Myeloma Working Group criteria after 8 cycles(31), progression free survival (PFS), duration of response and overall survival. Progression free survival, duration of response and overall survival will be estimated using the Kaplan-Meier method and reported along with 95% confidence intervals at appropriate time points.

A number of correlative studies will be performed in order to assess carfilzomib in vitro biological activity and investigate minimal residual disease in MM. Minimal residual disease will be further explored using multi-parametric flow cytometry and PET-CT imaging.

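### Sections 5.1.1.d and 5.1.2.b let two secondary-objective analyses be chosen or dropped once results are known, although 1.1.2, 1.2.8, the 5.1 table and 10.3.2 treat them as planned

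*Combined protocol and SAP*

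**What the plan says.** Section 5.1.1, item d, introduces the marrow correlatives by saying that they "will be performed and related to clinical outcome if the results of the study indicate a clinical or translational rationale for analyzing the samples". It continues: "Such studies may include but are not limited to the following". The list that follows includes immunohistochemistry (d.i), flow-cytometry MRD (d.ii) and CD138+ sorting with gene-expression profiling (d.vi).

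Section 5.1.2, under All Samples item b, has blood and urine analysed for biomarkers and "correlated to clinical outcomes if the results of the study indicate a clinical or translational rationale for analyzing the samples". Its list includes circulating-proteasome activity and apoptosis assays before and after carfilzomib.

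Section 1.1.2 gives six secondary objectives. One is "To assess the impact of minimal residual disease by flow cytometry and PET/CT in relation to outcome". Another is to evaluate the biological activity of carfilzomib and correlate it with clinical outcomes, "including gene expression profiling on pre- and post-carfilzomib exposure bone marrow samples". Neither carries a condition.

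Section 1.2.8 says: "Patients will also undergo evaluation for minimal residual disease at regular interval time points". Section 10.3.2 says: "A number of correlative studies will be performed in order to assess carfilzomib in vitro biological activity and investigate minimal residual disease in MM". The 5.1 table marks the flow and gene-expression rows as scheduled and labels other rows optional.

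**The concern.** A secondary objective that is promised without condition in one section should not depend on the study's results in another. If 5.1.1.d is followed as written, the team may look at the clinical results and then decide whether the relation of MRD, gene expression or carfilzomib activity to outcome will be analysed. An unpromising objective could go unanalysed and unreported with the protocol's permission. A reader who sees a reported association could not tell whether it was planned or was pursued because the results invited it. If the choice depended on the association itself, the reported estimate would tend to lie away from the null.

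**Working it through.** **The plan's own figures.** The only sizing figures concern the toxicity rule in 10.2, for X ~ Binomial(45, p). P(X ≥ 5) = 1 − Σ(x = 0 to 4) C(45, x) p^x (1 − p)^(45 − x). This gives 0.0729 at p = 0.05 (stated 7.3%) and 0.8252 at p = 0.15 (stated 82.5%). Both reproduce. Neither bears on this point, and the documents give no test, error rate or event count for the correlatives. The check is therefore a comparison of texts.

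**Step 1: scope of the condition.** The lead-in to 5.1.1.d governs two actions, performing the studies and relating them to outcome. It covers the whole list. Item d.vii has its own optional and exploratory labels, so the protocol can mark discretionary work separately, yet the lead-in is not confined to that item.

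**Step 2: what the condition leaves open for each analysis.**

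| Analysis | Running the assay | Relating it to outcome |
|---|---|---|
| Flow MRD (d.ii) | Not open in practice. It is a pre-treatment test in 2.4.1.1 and scheduled in the 5.1 table. Appendix B requires fresh aspirate to be processed without delay. The cycle 8 result makes later marrows (5.1.1.a) and PET scans (3.3.7.7) optional. | Open |
| Immunohistochemistry (d.i) | Not open in practice. It is scheduled in the 5.1 table, is one of two accepted methods for sCR in 6.3.3.1, and is used with flow in study-calendar note o to interpret CR. | Not a secondary objective in its own right |
| CD138+ gene expression (d.vi) | Open. It is marked at every time point in the 5.1 table, but d.vi ships samples in batches and makes molecular expression analyses subject to resources. | Open |
| Carfilzomib-activity measures (5.1.1.d, 5.1.2.b) | Proteasome activity and apoptosis assays are on the baseline lists in 2.4.1.1 and 2.4.1.2. In 5.1.2.b the condition can be read as attaching only to the correlation step. | Open |

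**Step 3: does the statistical section close the gap?** Section 10.3.2 gives Kaplan-Meier estimation for PFS, duration of response and OS. On MRD it says only: "Minimal residual disease will be further explored using multi-parametric flow cytometry and PET-CT imaging". It gives no time point, outcome, test or model for relating MRD or expression to outcome. The 5.1.1.d and 5.1.2.b sentences are thus the only rules on when that step happens.

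**Step 4: can results be known before the choice is made?** Yes. Section 1.2.10 reports best response and toxicity for the first 20 of 45 patients from a 2012 presentation. Batched samples can be assayed after such data exist. This shows opportunity only.

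**The case against.** The strongest reply is that 5.1.1.d is one loosely drafted lead-in, outweighed by the unconditional statements in 1.1.2, 1.2.8, the 5.1 table and 10.3.2. That supports saying that the text permits later selection, and no more. It does not remove the contradiction, because no section says which statement prevails.

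Three stronger readings are tempting, and the documents do not support them.

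- A reader might infer that flow MRD and immunohistochemistry are run only if the results look interesting. The schedule, the immediate processing and the use of MRD status during treatment rule this out. For flow MRD, only the outcome-relating step is open, but that step is the secondary objective.
- A reader might infer that analyses were in fact selected after outcomes were seen. Nothing in the documents shows this.
- A reader might want an inflated hazard ratio or false-positive rate. Such a figure assumes that the MRD-outcome association itself triggers the analysis. The text names no trigger. If the trigger were overall response or toxicity, selection need not depend on that association at all.

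Two practical objections also stand. Requiring gene expression on every scheduled sample would conflict with 5.1.1.d.vi and Appendix B, which omit CD138+ purification or sorting in CR or remission. It would also conflict with the resource proviso and with the discretion over research marrows given to the principal investigator from Amendment L. And deleting the condition alone would leave time point and method to be chosen later.

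Finally, the PET/CT half of the MRD objective lies outside 5.1.1.d. Its schedule in 5.1.4.1.1 carries no such condition.

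**Conclusion.** The point holds as a contradiction between sections that permits results-driven selection. It covers relating flow MRD to outcome, both running gene expression and relating it to outcome, and relating the carfilzomib-activity measures to outcome. These fall under two of the six secondary objectives in 1.1.2. No numerical size can be given, since the documents do not say which results trigger the work, who judges them, or when. The conclusion assumes only that 5.1.1.d and 5.1.2.b mean what they say. The primary toxicity endpoint, the 45-patient sample size and the Kaplan-Meier estimates are untouched. The sponsor should correct the wording, because the standing of stated secondary objectives depends on it.

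**What to change.** 1. In 5.1.1.d and 5.1.2.b, exempt the secondary-objective analyses from the results condition: flow MRD, CD138+ gene expression before and after carfilzomib, and the carfilzomib-activity measures.
2. State that their relation to outcome will be analysed and reported whatever the results, using all samples collected and processed under 5.1.1.d.vi and Appendix B. Say that no CD138+ sorting is required for patients in remission.
3. State that any assay not run for lack of resources will be reported as such, and that this decision will be made without reference to outcome.
4. In 10.3.2, name the time point, outcome and method for each. For example, use MRD at CR or at the end of cycle 8, with PFS counted from that landmark. Section 6.3.5 counts PFS from the start of treatment, so the landmark origin must be stated.
5. Keep the results-driven condition only for optional assays such as d.vii, and label them exploratory.

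This changes protocol wording and adds a short analysis paragraph. It changes no visit, sample, sample size or error rate. The cost is that the team can no longer drop a secondary-objective analysis once results are known.

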5.1.2 Research Blood/Serum and Urine

Blood:

- a. At any given time, up to 100cc of peripheral blood will be collected. The amount of blood collected will be dictated by the number of experiments to be performed, and by the patient's peripheral blood count.

Typical time points include: baseline, Day 2, Day 8 and Day 15 of Cycle 1, Day 1 of every cycle during cycles 2-8, Day 1 of every third cycle during cycles 9 and beyond during extended dosing phases (I and II), during Cycles 1-8 if CR is achieved or at the end of cycle 8, during cycles 9-20 if CR is achieved or at the end of cycle 20, during cycles 21-32 if CR is achieved or at treatment termination, and at any time point if the patient has progression of disease.

Samples may be collected within 2 days prior to each of the above time points during the induction phase; and within 7 days prior to each of the above time points during the extension phase I and II phase. This does not include the blood draws for

pharmacokinetic analysis as outlined below. Samples may also be collected every 3-6 months during the post-maintenance follow-up period.

- b. The standard number of peripheral blood research tubes drawn for collection and storage at each of the above timepoints may include but are not limited to the following: one 8 mL serum separator tube (SST), one 10 mL sodium heparin tube (GGT), and one 10 mL EDTA lavender top tube for storage in the Blood Processing Core (BPC) in 10/5A09 ([name] Lab) for biobanking. Additionally, up to six 10 ml EDTA tubes may be collected for various experiments to be performed with FDA collaborators, see below and one 6 mL EDTA lavender top tube for analysis and storage in the [name] Lab.

Urine:

- a. At any given time, approximately 45 mL of urine will be collected into a standard urine collection cup and sent for analysis and storage at each of the above time points.

Typical time points include: baseline, Day 2, Day 8 and Day 15 of Cycle 1, Day 1 of every cycle during cycles 2-8, Day 1 of every third cycle during cycles 9 and beyond during extended dosing phases (I and II), during Cycles 1-8 if CR is achieved or at the end of cycle 8, during cycles 9-20 if CR is achieved or at the end of cycle 20, during cycles 21-32 if CR is achieved or at treatment termination, and at any time point if the patient has progression of disease.

Samples may be collected within 2 days prior to each of the above time points during the induction phase; and within 7 days prior to each of the above time points during the extension phase I and II phase. The amount of urine collected will be dictated by the number of experiments to be performed.

All Samples:

- a. Collection and storage of peripheral blood and urine outlined in [Appendix C](#). Sample Requirements and Handling: The date and exact time of each blood draw should be recorded on the sample tube. Serum samples should be kept at room temperature for 30-60min prior to being refrigerated. Please e-mail [name] at [contact] and [name] [contact] at least 24 hours before transporting samples (the Friday before is preferred).

For sample pickup, page [name].

For immediate help, call [contact] (main blood processing core number) or, if no answer, [contact] (main clinical pharmacology lab number).

For questions regarding sample processing, contact [name] by e-mail or at [contact].

- b. Peripheral blood and/or urine samples from patients will be analyzed for potential serum or urine biomarkers as well as drug concentrations, and correlated to clinical outcomes if the results of the study indicate a clinical or translational rationale for analyzing the samples. Such biomarkers may include but are not limited to:
 - i. Peripheral blood flow cytometry assessing for circulating plasma cells under the direction of [name].
 - ii. Subunit profiling and activity of circulating proteasomes by enzyme-like

- iii. immunosorbent assay
- iii. Apoptosis assays pre and post-carfilzomib to identify necrotic or late stage apoptotic cells
- iv. Immunolocalization studies
- v. Markers of bone turnover and disease activity
- vi. Bone marrow, blood and urine samples, and associated clinical lab data will be sent to Adaptive Biotechnologies Corp for deep sequencing of the VDJ sequence.
- vii. Peripheral blood will be assessed for immune cell populations including, but not limited to T cells (CD4 and CD8), LGL, and NK cells using flow cytometry under the direction of [name]

5.1.3 Pharmacokinetic Samples

- a. PK Sampling Schedule: Samples will be collected at the following time points on C1D1: pre-dose, end of infusion, 5, 15, and 30 minutes and 1, 1.5, 2, 4, 6, and 24 hr post administration for carfilzomib. The plasma levels of lenalidomide will be collected on Cycles 2-8 D1 during induction phase and every 3 cycles during extended dosing with lenalidomide to determine steady-state lenalidomide levels.
- b. Sample Requirements and Handling: A venous blood sample will be collected in a 6-ml sodium heparin (green top) tube (BD Sodium Heparin 367878 or 367879) at each time point. Samples should immediately be placed on wet ice and refrigerated. The date and **exact** time of each blood draw should be recorded on the sample tube and the PK sheet. Questions regarding the collection of these samples can be directed to [name]. A 6.0 ml aliquot of whole blood will be spun to obtain the plasma, which will be kept frozen at -70°C until analysis. For sample pickup, page [name].

For immediate help, call [contact] (main blood processing core number) or, if no answer, [contact] (main clinical pharmacology lab number).

For questions regarding sample processing, contact [name] by e-mail or at [contact].

- c. Sample Analysis: The determination of lenalidomide and carfilzomib concentrations in all plasma samples, as well as the pharmacokinetic data analysis, will be performed by the Blood Processing Core (BPC) (For questions regarding sample processing, contact [name] by e-mail or at [contact]). Samples will be analyzed using a validated LC-MS/MS method developed at the end of the trial.
- d. Pharmacokinetic Analysis: Non-compartmental and compartmental pharmacokinetic and pharmacodynamic modeling of carfilzomib in plasma will be performed using WinNonlin 5.0 (Pharsight, Inc., Mountain View, CA). PK parameters derived from plasma concentration-time data may include C_{MAX} , T_{MAX} , AUC, CL, Vd, and $t_{1/2}$.

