3.2.2.2 Lenalidomide

- Cycle 1: 25 mg oral days 2-21 of 28-day cycle
- Cycle 2-8: 25 mg oral days 1-21 of 28-day cycle
- Lenalidomide capsules should be swallowed whole, and should not be broken, chewed or opened.

- If a dose of lenalidomide is missed, it should be taken as soon as possible on the same day. If it is missed for the entire day, it should not be made up.
- Patients who take more than the prescribed dose of lenalidomide should be instructed to seek emergency medical care if needed and contact study staff immediately.
- Lenalidomide (Revlimid®) will be provided to research subjects for the duration of their participation in this trial at no charge to them or their insurance providers. Lenalidomide will be provided in accordance with the REMS® program of Celgene Corporation. Per standard REMS® requirements all physicians who prescribe lenalidomide for research subjects enrolled into this trial, and all research subjects enrolled into this trial, must be registered in and must comply with all requirements of the REMS® program. Prescriptions must be filled within 7 days. Only enough lenalidomide for one cycle of therapy will be supplied to the patient each cycle.

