3.2.5 Extended Dosing Phase I: Cycles 9-20

- Patients that achieve a SD or better after 8 cycles of therapy will go on to receive extended dosing with oral lenalidomide 10 mg, given daily for 21 days of a 28 day cycle, for 12 cycles.
- Lenalidomide ordered in the extended dosing phase of the study will be prescribed monthly by NIH Clinical Center physicians. Upon completion of phone counseling per the REMS® program, the NIH Clinical Center physician will prescribe a 28 day supply of lenalidomide to be sent to the patient by express delivery.
- Females of childbearing potential (FCBP) patients will be required to have pregnancy testing as outlined in [Appendix A: Requirements for REMS®](#); and may have the pregnancy test performed by local treating physician. In these cases, the local physician will submit the results to NIH Clinical Center for review. Upon receipt of negative pregnancy test result and completion of phone counseling per the REMS® program, NIH Clinical physician will prescribe a 28 day supply of lenalidomide to be sent to the patient by express delivery.

3.2.6 Extended Dosing Phase II (optional): Cycles 21 through 32 (effective with Amendment H version date: 05/17/2013):

- After 12 cycles of extended dosing of lenalidomide (phase I), patients who maintain their current clinical response and do not meet criteria of PD as defined in [Section 6.3](#) will have the option to continue lenalidomide as clinically indicated for one additional year. For those patients who are ready to begin extended dosing phase II, treatment may be delayed until amendment H is approved by the IRB.
- Lenalidomide ordered in extended dosing phase II will be prescribed monthly by NIH Clinical Center physicians. Upon completion of phone counseling per the REMS® program, the NIH Clinical Center physician will prescribe a 28 day supply of lenalidomide to be sent to the patient by express delivery.
- FCBP patients will be required to have pregnancy testing as outlined in [Appendix A](#); and may have the pregnancy test performed by local treating physician. In these cases, the local physician will submit the results to NIH Clinical Center for review. Upon receipt of negative pregnancy test result and completion of phone counseling per the REMS® program, NIH Clinical physician will prescribe a 28 day supply of lenalidomide to be sent to the patient by express delivery.

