3.4 STUDY CALENDAR

Study	Pre-treatment	Induction Treatment							Extended Treatment				End of Treatment and Follow-Up	Disease Progression at any Time Point ^{l,p}
		Cycle 1					Cycle 2-8		Extended Dosing Phase (Phases I and II)				Every 3-6 months ^(j,p,r,s,t) or annual ^(v)	
		Day 1	Day 2	Day 8	Day 15	Day 22	Day 1 ^p	CR Achieved/End of Cycle 8 ^{m,n,o,p}	Day 1 of Cycles 9, 12, 15, 18, 21, 24, 27, 30 ^{c,e,r,s}	Day 1 Cycles 9, 12, 15, 18 ^{p,r,s}	Day 1 Cycles 9-32 ^{r,s}	Phase I-CR Achieved (Cycle 9-20)/ End of Cycle 20 and Phase II-CR achieved (Cycle 21-32)/ Treatment termination ^{m,n,o,p,r,s}		
Medical Record Review	x												x	
H&P	x	x	x	x	x	x	x		x					
ECOG	x						x		x					
Informed Consent	x													
Routine Labs ^a	x	x	x	x	x	x	x		x				x	x
Urine for UPEP and IFE ^m	x	x ^m					x ^m	x ^m	x ^m			x ^m	x	x
Viral Studies ^b	x													
Register for REMS®	x													
Pregnancy Test ^c	x ^c	x ^d	x ^d	x ^e	x ^e	x ^e	x ^c		x ^{c,e}		x ^{c,e}	x ^c	x ^e	
Myeloma Tests ^f	x						x		x			x ^q	x	x
Pharmacokinetic Studies		x ^k					x			x				
Research Blood/Urine	x		x	x	x		x	x	x			x ^r	x	x
Bone Marrow/Aspirate	x ^g		x ^h					x ^{i,o}				x ^{i,o}	x ⁱ	x
Skeletal Survey	x													
FDG PET-CT	x							x ⁿ				x ⁿ	x ⁿ	x
DW-MRI												x ^u		

the PI. In certain circumstances (at the discretion of the patient and PI), patients who are being followed by an outside oncologist and institution may continue to stay on study without a formal NIH visit, but by investigator-patient or investigator-physician phone or email communication to capture clinical and laboratory data. During the follow up phase, research blood/urine collection is optional and at the discretion of the PI.

- k. Pharmacokinetic studies Cycle 1 Day 1 will be collected at the following time points: pre-dose, end of infusion, 5, 15, and 30 minutes and 1, 1.5, 2, 4, 6, and 24 hours post administration for carfilzomib.
- l. At disease progression, marrow and FDG-PET/CT are optional.

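### Lenalidomide steady-state samples are scheduled for Day 1, after seven drug-free days, and the draw is not tied to the dose time

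*Combined protocol and SAP*

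**What the plan says.** Section 5.1.3 sets the induction schedule: "The plasma levels of lenalidomide will be collected on Cycles 2-8 D1 during induction phase". It continues the sampling "every 3 cycles during extended dosing with lenalidomide to determine steady-state lenalidomide levels". The study calendar (Section 3.4) agrees on the day. It marks pharmacokinetic studies at Day 1 of Cycles 2-8 and, in extended dosing, under the column "Day 1 Cycles 9, 12, 15, 18".

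The dosing sections set the drug days. Section 3.2.2.2 gives "Cycle 1: 25 mg oral days 2-21 of 28-day cycle" and "Cycle 2-8: 25 mg oral days 1-21 of 28-day cycle". Section 3.2.5 has extended dosing "given daily for 21 days of a 28 day cycle, for 12 cycles", and the table in Section 3.3.4 keeps the 21-of-28-day pattern in both extension phases.

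Section 5.1.3 asks for the exact time of each blood draw on the tube and the PK sheet. It does not say whether the lenalidomide draw comes before or after that day's capsule, and it does not ask for the time of the last dose. Its modelling paragraph covers carfilzomib only. Section 5.1.2 foresees that samples may be analysed for "serum or urine biomarkers as well as drug concentrations, and correlated to clinical outcomes", on condition that the study results give a clinical or translational reason to do so.

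**The concern.** The stated purpose and the sampling day do not fit together. Steady state belongs to the period of continuous daily dosing. Day 1 of a new cycle comes at the end of the off-drug week. A sample taken before the Day 1 capsule measures what is left after washout, and a sample taken after it measures a first dose following a break.

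Followed as written, the plan would report washout or first-dose values as steady-state levels. If they were then related to response or toxicity, differences between patients could reflect when the tube was drawn rather than exposure, and a true exposure-response relation could be missed. The volume is not trivial. There are 7 induction draws per patient plus 4 in extension by the calendar, or 8 if every third cycle runs through Cycle 30. For 45 patients who complete all of them, that is 11 × 45 = 495 to 15 × 45 = 675 samples.

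**Working it through.** The plan gives no figure to reproduce here. The check is schedule arithmetic plus first-order decay.

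**Inputs.** Drug days 1-21 of 28 (Sections 3.2.2.2, 3.2.5, 3.3.4); draw on Day 1 (Sections 5.1.3, 3.4); once-daily dosing. The half-life *t* is not in the documents, so it is an assumption, varied from 3 to 48 h.

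**1. Gap.** Drug-free days are 22-28, that is 28 − 21 = 7. From the Day 21 dose to the next Day 1 is 8 days × 24 = 192 h. Cycle 1 starts the drug on Day 2 but also ends it on Day 21, so Cycle 2 Day 1 has the same gap. The permitted 5-week delay for stem cell harvest can stretch the gap before Cycle 5 to 8 + 35 = 43 days.

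**2. Pre-dose draw.** A steady-state trough lies 24 h after a dose and the Day 1 pre-dose sample lies 192 h after one, so the extra decay time is 168 h. Share of the trough = 0.5^(168/*t*).

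**3. Post-dose draw.** Let *r* = 0.5^(24/*t*). In a bolus approximation, the peak after 21 daily doses, in units of one dose, is *A* = (1 − *r*^21)/(1 − *r*). Day 1 peak as a share of it = 1/*A* + 0.5^(192/*t*).

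| Assumed half-life | Pre-dose Day 1 / steady-state trough | Post-dose Day 1 / steady-state peak |
|---|---|---|
| 3 h | about 1e-17 | 99.6% |
| 6 h | about 4e-9 | 94% |
| 9 h | about 2e-6 | 84% |
| 12 h | 0.006% | 75% |
| 24 h | 0.8% | 50% |
| 48 h | 8.8% | 36% |

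The pre-dose share reaches 5% only at *t* = 168/log2(20) = 168/4.32, or about 39 h.

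**4. Unknown time since dose.** Where the half-life is short enough for the post-dose ratio to be near 1, the level itself moves fast. At *t* = 3 h, two post-dose draws 3 h apart differ by 0.5^(3/3), a factor of two.

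**5. Windows.** Calendar footnote r lets extension draws fall up to 7 days before Day 1, on Days 22-28 of the previous cycle. If the draw is made at the usual capsule hour, that is 24 h to 168 h after the last dose. At *t* = 24 h the level then runs from the full trough (Day 22) down to 0.5^(144/24) = 1.6% of it (Day 28). Footnotes p and s also allow later draws. If capsules start on time, those land on drug days. If the cycle start moves with the visit, the break only lengthens.

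**6. Dose change.** Cycle 9 Day 1 falls where the scheduled dose changes from 25 mg to 10 mg, so a draw there is at steady state for neither.

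**7. Would a mid-cycle draw serve?** A Day 15 pre-dose sample follows 14 daily doses. Share of the eventual trough = 1 − 0.5^(14 × 24/*t*). At *t* = 48 h this is 1 − 0.5^7 = 99.2%, and it is higher for any shorter half-life.

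**The case against.** The best counter-argument is the right-hand column of the table. If the draw is post-dose and the half-life is a few hours, there is almost no accumulation and a first-dose level nearly equals a steady-state one. That stands. A reader might infer that Day 1 samples can never reflect steady state, carry no information on exposure and are wasted. The documents do not support this, because they give no half-life and do not say that the draw is pre-dose. The same silence is why the counter-argument does not rescue the plan: a post-dose value can be read only with its time since dose, and the text does not require that time. The PK sheet may have a field for it, but the sheet is not in the documents.

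The windows also count against calling every sample washout. A Day 22 draw could be a true trough, and a late draw could fall on a drug day. The result is inconsistent sampling, which is a different fault.

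A reader might also infer that the trial is committed to an exposure-outcome analysis. It is not: Section 5.1.2 makes that conditional. Lenalidomide levels appear in none of the objectives in Section 1.1 and nowhere in Section 10, so the toxicity endpoint, the stopping rule and the 45-patient target are untouched.

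Finally, Section 13.1.1 describes the carfilzomib supply in the past tense, so induction sampling may be over. That limits which part of the fix can still be used. It does not settle how the samples should be labelled, since Section 5.1.3 leaves the assay method to the end of the trial.

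**Conclusion.** The point holds as an internal mismatch: the draw day in Section 5.1.3 and the calendar does not deliver the steady-state purpose under the dosing schedule in Sections 3.2.2.2 and 3.2.5. The seven-day break and the 192 h gap come straight from the schedule and need no assumption. The residual levels do rest on assumptions: an unstated half-life, first-order decay and a bolus approximation. Within those, a pre-dose Day 1 sample is below 5% of the trough for any half-life under about 39 h. A post-dose sample is a first-dose level that stands in for the steady-state peak only when the half-life is short and the time since dose is known. The consequence is confined to a correlative measure with a conditional link to outcomes. It is worth correcting because the correction is cheap and the present label would misdescribe the data.

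**What to change.** - **Induction.** In Section 5.1.3 and the calendar, move the lenalidomide sample to a draw before that day's capsule at an existing mid-cycle infusion visit, for example Day 15 of Cycles 2-8 (Section 3.2.2.1 already schedules carfilzomib that day). Record the time of the last lenalidomide dose next to the draw time.
- **Extension.** Draw only when the visit falls on a drug day, again with the last dose time recorded, or drop these samples.
- **Samples already collected on Day 1.** Drop the steady-state label and report them by time since last dose where records allow. If induction is complete, this is the part that still applies to those samples.

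The cost is small but more than wording. The calendar now shows only a Day 1 visit for Cycles 2-8, so it needs one added entry. Patients need an instruction to take that day's capsule after the draw. The tube count does not rise and no induction visit is added. The change concerns sampling and labelling only and implies no change to dosing.
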